1. OVERVIEW

1.1 Executive Summary

The use of antibiotics has saved millions of human lives, however consumption of antibiotics can select for antibiotic resistant organisms and may lead to changes in commensal microbiome. Here, we propose a series of studies designed to estimate the effect of antibiotic consumption on antibiotic resistance and microbiome in a region of rural Burkina Faso. In Study One, we will measure antibiotic consumption at the community level and estimate the relationship between community-level antibiotic consumption and community-level pneumococcal resistance. In Study Two, we will measure changes in the intestinal and nasopharyngeal microbiome and resistome following a short course of antibiotics.

1.3 Study Sites

This study will take place within the Nouna Health and Demographic Surveillance Site (HDSS). The HDSS covers an area of 1,775 km², covering 103,576 individuals living in 58 villages as well as the town of Nouna. For **Objective 1**, we will include 20 villages served by 6 health centers: Bourasso, Sikoro, Labarani, Lekuy, Nokuy Bobo, and Kodougou in the southeast of the HDSS. For **Objective 2**, we will include the villages of Dara and Kamadena in the western region of the HDSS. To avoid contamination between studies, the two study areas will not overlap.

2. BACKGROUND

Azithromycin and other antibiotics are being considered for routine use in settings with high burdens of child morbidity and mortality. In Burkina Faso, the under-5 child mortality rate is 110 per 1,000 live births, which is among the highest child mortality rates in the world.¹ The major causes of child mortality in Burkina Faso are infectious: upper respiratory tract infection, diarrhea, and malaria.^{1,2} Furthermore, malnutrition is a major contributor to child mortality and morbidity, with an estimated 35% of children malnourished in rural Burkina Faso.³ Antibiotics may therefore reduce child morbidity and mortality by treating underlying (often subclinical) infections. *We propose to conduct this study in a region of rural Burkina Faso where the burden of child mortality and morbidity is high, and child deaths are attributable to upper respiratory tract infection, diarrhea, malaria, and malnutrition.*

Mass azithromycin distribution for trachoma control may lead to substantial decrease in child mortality.⁴ A recent study in rural Ethiopia noted a nearly 50% decrease in child mortality in communities that had received a single mass azithromycin distribution for trachoma control. The use of antibiotics may also contribute to improved growth and nutrition outcomes for children in regions with a high burden of malnutrition.⁵ Amoxicillin is used routinely as part of outpatient treatment of acute malnutrition. Randomized controlled trials of amoxicillin as adjunctive therapy for malnutrition has found that children receiving antibiotics gain more weight over an 8-week period compared to children receiving placebo.^{6,7} Cluster-randomized trials of community-based management of pneumonia with co-trimoxazole found significantly lower all-cause under-5 mortality in communities receiving the co-trimoxazole intervention.⁸ Amoxicillin and co-trimoxazole are also used for prevention of lower respiratory tract infections in high-risk children.⁹ A recent systematic review and meta-analysis of antibiotic use in children in low- and middle-income settings found a consistent, strong association between antibiotic use and reduced prevalence of wasting and stunting, both among children with and without clinical indication for antibiotics.⁵ We recently performed anthropometric analyses on children randomized to azithromycin versus no treatment for trachoma and found a statistically significant improvement in height among children treated with antibiotics (manuscript in preparation).

Millions of doses of azithromycin are distributed in predominantly rural Sub-Saharan African settings for trachoma control as part of mass azithromycin distribution programs. In addition to drastically reducing the prevalence of trachoma globally¹⁰⁻¹⁶, previous work has shown that azithromycin distributed as part of trachoma control programs has led to decreases in diarrhea^{17,18}, skin infections, lower respiratory infection¹⁹, and malaria²⁰, in addition to all-cause mortality.⁴ On the other hand, the risks of mass azithromycin distribution are largely confined to non-serious adverse events, including abdominal pain, nausea, and vomiting²¹, and transient increase in community resistance, a resistance which has never been shown to be clinically meaningful and resistance levels return to normal levels when antibiotic selection pressure is removed.^{22,23}

There is a potential for unintended consequences with the use of antibiotics, including reduced bacterial diversity. Antibiotics may alter the host's commensal microbiota.^{22,24-29} A recent study among antibiotic-naïve children in Niger found a significant decrease in bacterial

diversity in children receiving a single dose of azithromycin compared to placebo²⁴, although this study did not evaluate long-term changes in microbiome following an antibiotic course. To date, there have been very few randomized assessments of changes in intestinal microbiome following a course of antibiotics, and thus the causal changes in microbiome are understudied. Furthermore, any functional differences due to altered microbiome remain as-yet unknown, as microbiome studies are in their infancy and mechanistic studies are lacking. Children with malnutrition have been shown to have decreased intestinal bacterial diversity.³⁰ This association is thought to be a result of poor diet and increased susceptibility to infection that leads to structural changes in the gut, poor absorption of nutrients, and subsequently altered microbiome.³¹ Furthermore, environmental enteric dysfunction is thought to be widespread in rural Sub-Saharan Africa. This condition is mediated in part by chronic infection with gram negative bacteria, and causes morphologic changes in the intestines that lead to malabsorption and subsequent malnutrition and stunting.³²⁻³⁴ Presumptive treatment with antibiotics may modulate the association and lead to intestinal microbiome changes that are actually beneficial for child health.

We propose two studies designed to gain a better understanding of the mechanisms behind the potential benefits and consequences of antibiotic use in settings with high child mortality and morbidity. We specifically propose to study these outcomes in children aged 6-59 months, as they are by far at the greatest risk of mortality due to infectious causes and are at the highest risk of malnutrition, and thus would benefit the most from child morbidity and mortality interventions. To date, there have been very few randomized assessments of changes in the intestinal microbiome following a course of antibiotics, and thus the causal changes in microbiome are understudied. We propose two studies to 1) understand the effect of community antibiotic consumption on community antibiotic resistance and 2) the effect of a short course of routine antibiotics on changes in intestinal and nasopharyngeal microbiome and resistome. We hypothesize that communities with higher antibiotic consumption will have higher prevalence of pneumococcal resistance in nasopharyngeal samples. Furthermore, we hypothesize that a short course of antibiotics will lead to decreased bacterial diversity shortly after completion of the antibiotic course, and higher probability of identification of bacterial resistance genes in rectal and nasopharyngeal samples.

3. STUDY DESIGN

We propose two studies to address the proposed objectives. **Study One** will be a cross-sectional, observational study designed to assess the relationship between community antibiotic consumption and pneumococcal resistance prevalence. **Study Two** will be a four-arm randomized controlled trial designed to yield estimates of the effect of a short course of antibiotics on intestinal and nasopharyngeal microbiome diversity and resistome.

3.1 Study One: Community antibiotic consumption and prevalence of pneumococcal resistance

Study One is a cross-sectional assessment of community antibiotic consumption and nasopharyngeal pneumococcal resistance. The study will occur in two phases.

During Phase I, we will extract data from routinely-collected Prescription Sheet from 6 health centers located in the Nouna HDSS. These prescription sheets are collected and stored at the health facility for all children under the age of 5. The sheets are taken to the pharmacy when the caregiver fills a prescription for the child. We will extract antibiotic prescriptions (and dispensing, as these sheets are filled when the caregiver picks up the prescription) for a period covering approximately 6 months (January through June, 2017). We will extract the following data on a standardized, electronic data collection form (see Section 8, Data Collection and Management):

- Health facility name
- Date of prescription
- Village of residence of the child
- Child's age
- Child's sex
- Antibiotic
- Dose and duration of antibiotic

To calculate antibiotic consumption, we will calculate the total doses of antibiotics and standardize using the size of the village per the most recent HDSS census.

During Phase II, we will determine pneumococcal resistance in a random sample of 15 children aged 6-59 months in each village in the catchment area for each health facility (e.g., each village for which antibiotic data were collected during Phase I). Children will be randomly selected for inclusion based on the most recent HDSS census. Nasopharyngeal swabs will be collected from each randomly-selected child, which will be processed via Kirby-Bauer disc diffusion assay at the CRSN microbiology laboratory (see Section 4 for details on specimen collection and Section 6 for details on microbiological methods). In addition, we will perform conjunctival photography and clinical evaluation of the conjunctiva on each enrolled child for rapid assessment of trachoma prevalence in each village, if a child is diagnosed with active trachoma the guardian will be given a tube of tetracycline. Caregivers of children randomly selected for inclusion in the study will additionally complete a brief antibiotic use survey.

3.1.1 Sample Size

A total of 6 health facilities and 20 villages will be included in Study One. We will collect nasopharyngeal swabs from 300 children in the 20 villages. Duplicate swabs will be collected on 2 children per village, so a total of 320 swabs will be collected.

3.1.2 Health Center and Community Eligibility

All health centers in the HDSS will be eligible for inclusion. We select health centers based on their accessibility during the rainy season, and select communities in a contiguous area of the HDSS. All villages in the catchment area of the health facility that are in the HDSS will be included.

3.1.3 Individual Eligibility

Children residing in the villages in the catchment area of included health facilities during the last census who are 6-59 months will be eligible for random inclusion in the study. We will use the census to randomly select 15 children aged 6-59 months of age from each village. If the child has moved out of the village or died since the last census, we will randomly select another child from the census.

3.2 Study Two: Antibiotic treatment and microbiome changes in children

Study Two is a randomized trial of a short course of antibiotics (azithromycin, co-trimoxazole, or amoxicillin) compared to no treatment. We will assess the effect of a short antibiotic course on intestinal and nasopharyngeal bacterial diversity and will test for antibiotic resistance in the resistome. Households with at least 2 children aged 6-59 months will be randomized in a 1:1:1:1 fashion to one of four study arms: 1) azithromycin, 2) amoxicillin, 3) co-trimoxazole, or 4) no treatment. All children minus one in the household will be treated, and we will assess the indirect effect of antibiotic treatment on the untreated child residing in the household. We will measure changes in microbiome three days following completion of the antibiotic course (primary outcome). During the final sample collection we will also complete a brief survey about the children's health particularly about diarrhea and respiratory infections. Finally, 4 weeks after the completion of the treatment we will evaluate the children's growth by doing anthropometric measurements.

3.2.1 Sample Size

We will enroll 120 households into the four study arms (30/arm).

3.2.2 Baseline Measurement

After enrollment and informed consent but prior to randomization, children will undergo anthropometry (height, weight, and mid-upper arm circumference measurements). Caregivers will complete a brief baseline survey that will include information on whether the child is currently exclusively breastfeeding, is currently experiencing diarrhea (measured by the standard WHO question, "Has the child had 3 or more loose or watery stools in the previous 24 hours"), and, for non-exclusively breastfeeding children, the child's dietary diversity.

3.2.3 Randomization

A list of potentially eligible households will be generated from the most recent census. This list will be sent to the study biostatistician ([name]), who will generate the randomization list. The randomization list will be 1:1:1:1 and will be generated without stratification or blocking.

The randomization list will contain the randomization arm and household identification number and will be transmitted to the field coordinator at CRSN.

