3.2.4 Community Eligibility

We will select two communities that have at least 120 households with 2 or more children under age 6-59 months at the most recent census. Children who are allergic to any of the study medications will not be enrolled in the study. Children who are receiving antibiotics for an ongoing disease won't be included in the study

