Antibiotic Resistance and Microbiome in Children Aged 1-59 months in Nouna, Burkina Faso

Manual of Operations and Procedures

NCT number 03187834

Version 1.1 June 2017

Centre de Recherche en Santé de Nouna

University of Heidelberg

Francis I. Proctor Foundation, University of California, San Francisco

Antibiotic resistance and Microbiome in Children Aged 6-59 months in Nouna, Burkina Faso

Statistical Analysis Plan, Version 1.0, June 15 2017

Study Overview

We will randomize 120 households containing 2 or more children aged 6-59 months to one of four study arms: 1) azithromycin, 2) amoxicillin, 3) cotrimoxazole, or 4) placebo. All children will receive 5 days of treatment. Full intervention details can be found in the Manual of Operations and Procedures. Rectal and nasopharyngeal swabs will be collected pre-treatment (baseline) and on Day 9 following the 5 days of treatment. Anthropometric indices (weight, height, and mid-upper arm circumference) will be collected at baseline and Day 35 (one month following treatment completion).

Randomization

The 120 households will be randomized in blocks of size 8 to one of the four treatment arms. In households randomized to treatment, all children aged 6-59 months of age will be treated, with the exception of one random child from within the household who will receive placebo. All children aged 6-59 months in households randomized to placebo will receive placebo. A random treated child from antibiotic arm households will be selected as the sentinel child for outcome assessment, and the untreated child from antibiotic arm households will also receive outcome assessment. Two children will be randomly selected from placebo households for outcome assessment.

Primary Outcome

We will compare diversity across arms at Day 9 and between time points. The primary outcome will be Simpson's index of alpha diversity. We will compare the mean Simpson's index between treatment arms with a t-test. All *P*-values will be calculated via permutation test.

Secondary Outcomes

As a secondary outcome, we will compare Shannon's index (L1 norm) between time points using a t-test. To compare if treatment significantly explains difference between the four treatment groups, we will compare Simpson's index (L1-norm) and Shannon's index (L2-norm) distances using PERMANOVA on bacterial reads.

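### Study Two does not fix when a household is randomised: arms are listed against census household IDs and sent to the field with no concealment step, so selective enrolment is possible and 30 per arm is not assured

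*Protocol*

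**What the plan says.** Protocol 3.2.3 (Randomization) describes the steps in this order. First, "A list of potentially eligible households will be generated from the most recent census". The study biostatistician then generates the allocation, and "The randomization list will contain the randomization arm and household identification number and will be transmitted to the field coordinator at CRSN". On method, "The randomization list will be 1:1:1:1 and will be generated without stratification or blocking".

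Protocol 3.2.2 (Baseline Measurement) gives a different order: "After enrollment and informed consent but prior to randomization, children will undergo anthropometry". The footnote to the schedule in 3.2.7 agrees with 3.2.2, placing randomisation on Day 0 once baseline assessments are finished.

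Several conditions for entry can be settled only at the household. Section 3.2.5 requires at least two children aged 6-59 months living there now. Section 3.2.4 excludes children with an allergy to a study drug or already on antibiotics. Section 8 requires written consent for Study Two.

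On numbers, section 3.2.1 says "We will enroll 120 households into the four study arms (30/arm"), and section 3.2.4 says "We will select two communities that have at least 120 households with 2 or more children under age 6-59 months at the most recent census". The SAP's Randomization paragraph says "The 120 households will be randomized in blocks of size 8 to one of the four treatment arms".

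**The concern.** A list that joins arm to household ID is already an allocation. If it is drawn from the census, each household has its arm before anyone has checked who lives there now, whether a child is excluded, or whether the parent consents. The list goes to the field coordinator, and nothing says that the arm stays hidden until a household has been enrolled.

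Two things are at stake. The first is concealment. Someone who knows the arm can, deliberately or not, press harder for consent in some households, apply the exclusions more or less strictly, or choose which household to visit next. When the next household already carries an arm, choosing the household also chooses the arm. The comparison of diversity between arms relies on this not happening.

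The second is the randomised set. If a household counts as randomised when the list is made, those that have moved, prove ineligible or refuse are exclusions after allocation. If it counts as randomised on Day 0, they are screening failures. The documents support both readings, and the SAP defines no analysis set that would settle the matter.

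**Working it through.** **Order of events, side by side**

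| Source | Arm assigned | Eligibility and consent |
|---|---|---|
| Protocol 3.2.3 | When the list is generated from the census | Not mentioned; listed households are only possible candidates |
| Protocol 3.2.2 | After enrolment, consent and anthropometry | Before the arm |
| Protocol 3.2.7, footnote | Day 0, after all baseline assessments | Before the arm |
| SAP, Randomization | Not timed; refers to the 120 households | Not mentioned |

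The first row agrees with the next two only if the prepared list is kept sealed and opened household by household on Day 0. No such step is described.

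**The stated split**

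Inputs: 120 households and four arms (3.2.1); blocks of 8 (SAP).
- 120 / 4 = 30 per arm.
- 120 / 8 = 15 complete blocks; 8 / 4 = 2 households per arm per block; 15 x 2 = 30 per arm.

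The SAP's blocking therefore reproduces 30 per arm exactly. The total of 120 cannot be re-derived, because 3.2.1 gives no effect size, SD, power or allowance for loss.

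**The split without blocking**

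If 3.2.3 means simple randomisation of 120 households (an assumption):
- P(30 in every arm) = 120! / (30!^4 x 4^120) = 0.0008.
- SD of one arm's size = sqrt(120 x 0.25 x 0.75) = 4.7.
- Smallest arm, by simulation: median 25, 95% range 19 to 29.

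An unblocked list could instead be one shuffled list with fixed 1:1:1:1 totals. That gives 30 per arm only if exactly 120 households are listed and all enrol.

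**Loss before enrolment**

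This applies only if the list holds exactly 120, arms start at 30 and nobody is replaced. The loss rate d is assumed. Expected number per arm = 30(1 - d); SD = sqrt(30 x d x (1 - d)). Power is for a pairwise difference that 30 per arm would detect with 80% power: (1.960 + 0.842) x sqrt(2/30) = 0.72 SD, two-sided 5%, normal approximation, ignoring household clustering. The last column is 120 / (1 - d), rounded up.

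| d | Households | Per arm | SD per arm | Power | List needed for 120 |
|---|---|---|---|---|---|
| 0% | 120 | 30 | 0 | 80% | 120 |
| 10% | 108 | 27 | 1.6 | 76% | 134 |
| 20% | 96 | 24 | 2.2 | 71% | 150 |

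A longer list worked through until 120 households enrol would reach the total. It would not by itself give 30 per arm, and with arms already attached it leaves open who picks the next household.

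**The case against.** The strongest reply is that 3.2.2 and 3.2.7 state the intended order plainly, and that a list prepared in advance but opened only on Day 0 is compatible with both. Households that have moved, are ineligible or refuse would then be screening failures. This stands as a possible reading, but it needs concealment, which 3.2.3 does not provide: arm and household ID go to the field coordinator together. The masking of laboratory staff in section 7 protects the assay and does not protect enrolment.

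A second reply is that moving away, ageing out, allergy and current antibiotic use are facts that the arm cannot influence. This also stands. Losses that are blind to arm cost precision and do not bias the comparison; bias requires someone to know the arm while entry is still being decided.

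A reader might infer that 120 households will not be reached. The documents do not support that. The 120 is a number to be enrolled, the community criterion is a minimum that may even apply to each community separately, and the list length is not given.

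A reader might also take the Study One rule ("If the child has moved out of the village or died since the last census, we will randomly select another child from the census") to show that Study Two needs a replacement rule. It shows only that the protocol expects movement since the census. Study One is a survey sample without allocation, and not replacing randomised units is normal practice.

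**Conclusion.** The point holds as a contradiction about when randomisation happens, combined with missing concealment, list length and contact order. The more serious consequence is that the arm can be known while eligibility, consent and the next household are being decided. Its effect on the results cannot be quantified from the documents, and nothing in them shows that selective enrolment took place.

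The effect on numbers is conditional and moderate. About 27 and 24 per arm at 10% and 20% loss, with illustrative power of 76% and 71%, rest on an assumed loss rate, a list of exactly 120 and no replacement. The conflict between the unblocked list in 3.2.3 and the SAP's blocks of 8 puts the 30 per arm at risk even with no loss: under simple randomisation an arm's size has an SD of 4.7.

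A reader might go further and infer that every household that drops out is a biasing post-randomisation exclusion. That would require randomisation to be defined as the making of the list, and the documents leave exactly this open. The supportable conclusion is that 120 households at 30 per arm is not assured, and that the plan should be corrected.

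**What to change.** Reword protocol 3.2.3 and the SAP's Randomization paragraph so that they agree with 3.2.2 and 3.2.7:

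1. Use the census only to produce a randomly ordered contact list of candidate households in the two villages, and state its length.
2. Attach arms to enrolment sequence numbers 1-120, not to household IDs.
3. Have the sequence held by someone who does not enrol households. Reveal each arm only after eligibility, consent and baseline are complete, and define that moment as randomisation.
4. Log households that have moved, are ineligible or refuse as screening failures. They use no allocation, and contact continues down the list until 120 are allocated.
5. State one blocking rule in both documents. The SAP's blocks of 8 give exactly 30 per arm over 120 allocations.
6. Replace no household after allocation, and analyse all 120 in the arm allocated.

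A sealed list linked to household IDs with a fixed contact order would also restore concealment, but households lost before enrolment would still take arms with them and disturb the balance.

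The cost is small. The number enrolled is unchanged; households must be contacted in list order and a screening log kept. The timetable allows it: randomisation is on Day 0, treatment starts on Day 1, and section 3.2.6.2 has syringes prepared on the day of administration from the baseline weight, so no described step needs the arm sooner.

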3.2.7 Study Schedule

| | Day 0 | Day 1-5 | Day 9 | 4 weeks after treatment completion |
|----------------|--------------|----------------|--------------|---|
| Enrollment | X | | | |
| Anthropometry | X | | | X |
| Swabs | X | | X | |
| Randomization* | X | | | |
| Treatment | | X | | |
| Outcome survey | | | X | |

*After all baseline assessments are complete

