7. MICROBIOLOGICAL METHODS

Participant names will not be included in laboratory records and samples will be de identified. Therefore, laboratory personnel will be masked, preventing identification of the individuals infected. Lab results will not be available for weeks, if not months. Thus, all individuals will be treated according to their study arm, whether or not their lab tests reveal evidence of infection.

Preparation of Zymo DNA/RNA Shield™

Manufacturer's Product Description

DNA/RNA Shield™ ensures nucleic acid stability during sample storage/transport at ambient temperatures, preserving the genetic integrity and expression profiles of samples. There is no need for refrigeration or specialized equipment. DNA/RNA Shield™ effectively lyses cells and inactivates nucleases and infectious agents (virus), and it is compatible with various collection and storage devices (vacuum tubes, swabs, nasal, buccal, fecal, etc.).

Materials Required

| Product | Supplier | Catalog No. |
|--|---------------------|--|
| DNA/RNA Shield™ 1X solution | Zymo Research Corp. | R1100-50 (50 ml) R1100-250 (250 ml) |
| 2ml Loop Screw Cap Micro Tube, PCR Performance Tested (DNA-, DNase-, RNase-, & PCR inhibitor-free) | Sarstedt Inc. | 72.694.416 |
| Insert for Loop Screw Cap, Violet | Sarstedt Inc. | 65.713.007 |

Procedure

1. Prepare tubes by adding violet cap inserts to the top of each tube (these are for color coding purposes to help distinguish the DNA/RNA Shield solution from other media being used in the field).
2. Before aliquoting the DNA/RNA Shield, gently mix the solution by either swirling it or inverting the bottle a few times (trying not to create too many bubbles) to ensure that the solution is homogenous. In a clean biosafety cabinet, use sterile technique to aliquot 1 ml of the solution into each 2 ml tube.
3. When you have finished aliquoting, make sure that the cap on each tube has been tightened to prevent tubes from leaking during transport.

Storage and Shelf Life

Store prepared tubes at room temperature (20°C-25°C) until use; do not freeze solution prior to collecting samples. Zymo guarantees the shelf-life of DNA/RNA Shield™ up to 1 year from the date of receipt. Therefore, if the solution is aliquoted right away, then prepared tubes should be good for 1 year. The shelf-life may be longer, depending on storage conditions.

Methods for Resistance Testing

Isolation & Identification of Organisms Using Microbiological Techniques

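### Protocol and SAP give different randomisation schemes (no blocking v blocks of 8), and no written step withholds each household's arm until consent and baseline are complete

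*Protocol*

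**What the plan says.** **Scheme.** Protocol 3.2.3: "The randomization list will be 1:1:1:1 and will be generated without stratification or blocking". SAP, Randomization: "The 120 households will be randomized in blocks of size 8 to one of the four treatment arms". Both are current text; neither comes from a summary of changes.

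**Test.** SAP, Primary Outcome, compares mean Simpson's index between arms with a t-test and says that all P-values "will be calculated via permutation test". It does not say what is permuted, or whether permutation is restricted to blocks.

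**List.** Protocol 3.2.3 begins: "A list of potentially eligible households will be generated from the most recent census". The study biostatistician generates the allocation from it, and then: "The randomization list will contain the randomization arm and household identification number and will be transmitted to the field coordinator at CRSN".

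**Timing.** Protocol 3.2.2: "After enrollment and informed consent but prior to randomization, children will undergo anthropometry". The footnote to the schedule in 3.2.7 places randomisation on Day 0, "After all baseline assessments are complete".

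**Masking.** The only masking explicitly described is in Protocol 7: "laboratory personnel will be masked, preventing identification of the individuals infected".

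**The concern.** There are two separate problems.

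The first is a contradiction. A permutation test takes its reference distribution from the set of allocations that could have occurred. With blocks of 8 that set is restricted; without blocking it is not. Until one scheme is chosen, the primary test is not fully specified.

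The second is concealment. The list is built from households that are only potentially eligible, and it already pairs household ID with arm when it goes to the field. Current residence (Protocol 3.2.5) and current antibiotic use (3.2.4) can be settled only at the visit, and consent is sought there too. If the arm could be seen at that point, two routes to bias would open:

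- **Selective enrolment.** Who is approached, judged eligible or persuaded could depend on arm. This can affect every outcome, including Day 9 Simpson's index. Laboratory masking does not touch it and analysis cannot repair it.
- **Arm-influenced measurement.** Baseline anthropometry is taken by field staff and is the covariate in the growth ANCOVA (SAP, Secondary Outcomes).

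**Working it through.** **1. The plan's own figure.** Protocol 3.2.1 gives 120 households, 30 per arm. 120/4 = 30. With blocks of 8 and equal allocation, 120/8 = 15 blocks, and 15 × 2 per arm = 30. Both agree.

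**2. What each reading delivers.** No effect size, SD or power is stated, so I assume a standardised difference of 0.736, which gives 80% power at 30 v 30 (two-sided 5%, t-test).

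- *Blocks of 8, all 120 allocated in order:* exactly 30 per arm, 80% power.
- *Unblocked, as one equal-arm permutation of exactly 120:* also 30 per arm, 80% power.
- *Unblocked, as independent draws:* SD per arm = √(120 × 0.25 × 0.75) = 4.74. The smallest arm averages 24.5 (simulation). Power averaged over the draws is 79.0%; a particular split of 24 v 36 gives about 78%.

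**3. If the household-ID list is itself the assignment.** Protocol 3.2.4 requires only that the two communities have at least 120 qualifying households, so the list may be longer than 120. Households that refuse or fail checks then take their arm with them. For a list of N in whole blocks of 8, with 120 enrolling regardless of arm, SD per arm = √(120 × 0.25 × 0.75 × (N − 120)/(N − 1)). The list lengths are assumptions.

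| N | SD per arm | Mean smallest arm | Mean power |
|---|---|---|---|
| 128 | 1.19 | 28.5 | 79.9% |
| 144 | 1.94 | 27.6 | 79.8% |
| 160 | 2.38 | 27.1 | 79.7% |
| 200 | 3.01 | 26.4 | 79.6% |

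Blocking therefore does not secure 30 per arm in this case, but the cost is small.

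**4. Blocks used but ignored in the test.** I simulated 40,000 trials with 15 blocks, two households per compared arm per block and one child per household. An ordinary t-test stands in for unrestricted permutation, and a block-adjusted t-test (44 df) for permutation within blocks. The block ICC is unknown and is assumed.

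| Block ICC | Type I error, blocks ignored | Type I error, blocks respected | Power, ignored | Power, respected |
|---|---|---|---|---|
| 0 | 4.9% | 4.9% | 79.9% | 79.5% |
| 0.1 | 3.9% | 5.0% | 81.6% | 83.9% |
| 0.3 | 2.2% | 5.0% | 84.5% | 91.6% |

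The mismatch never inflates false positives. It loses power only if households in the same block resemble each other; at ICC 0 nothing is lost.

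**5. Concealment, by reading.** Sections 3.2.2 and 3.2.7 fix an order: consent, baseline, randomisation. Section 3.2.3 describes an arm already attached to each household ID on a list sent to the field. Nothing reconciles the two: no sealed envelope, call, electronic release, or separation of the list holder from staff who enrol and measure. The size of any resulting selection bias cannot be calculated from the documents.

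**6. Predictability of fixed blocks.** With two of each arm in a block of 8 and all earlier arms known, the last assignment is always determined. The last two are both determined when they share an arm, which has probability 1/7. The average is 1 + 1/7 = 1.14 of 8 (14%), and any one block has either 1 or 2.

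**The case against.** The provable half is small. It causes no bias, costs little power through arm sizes, and leaves at worst a conservative test; all those figures rest on assumed inputs. This stands.

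The concealment half argues from silence. The order is stated twice, Protocol 3.2.3 gives no date for sending the list, and nothing says the field coordinator enrols or measures children. Section 3.2.6.2 has staff at CRSN prepare the syringes and mentions child and household ID on the label but no arm, so those who plainly need the arm are the preparers. A release step may exist elsewhere. This stands as a limit on what can be claimed. It does not supply the missing step.

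The measurement route is also narrow. Length or height and weight are each taken three times on instruments; only MUAC is measured once. The primary Day 9 comparison does not use them. A reader might infer that arm-influenced scores on the baseline developmental checklist (DMC-III) would bias a result, but DMC-III enters no analysis in the SAP.

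Finally, withholding the arm until every Day 0 item is done could collide with the Day 1 start. Protocol 6 defers DMC-III observation in an unwell child to a later date, and Protocol 4.2 allows some stool to be collected the next morning. This also stands, and the release rule must allow for it.

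**Conclusion.** The contradiction is certain and should be resolved before the list is generated. On its own it is minor: no bias, and about one point of power on average under the least favourable arm-size reading at the assumed effect. If blocks are used, ignoring them makes the primary test conservative to a degree set by an unknown block ICC.

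The concealment gap matters more but is held with moderate confidence. A reader might infer that enrolling staff knew the arms, or that enrolment was in fact selective. The documents do not support that: they show an arm-by-household list going to the field coordinator and a timing rule with no mechanism behind it, and no more. A reader might also infer that the scheme conflict invalidates the primary test; the simulation above shows only loss of power, not excess false positives. Taken together, this should be fixed.

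**What to change.** 1. State one scheme in both documents. If blocks are kept, remove the exclusion of blocking from Protocol 3.2.3. If not, remove the block size from the SAP and say whether the list is one equal-arm permutation of 120 or independent draws.
2. In SAP, Primary Outcome, specify that the permutation test re-randomises households under that scheme, within blocks if blocked.
3. In Protocol 3.2.3, have the statistician, or another person not involved in enrolment or measurement, hold the list and release each household's arm only after consent and the baseline anthropometry, survey and swabs are recorded. State how deferred DMC-III observation, or next-morning stool if it is collected in Study Two, is handled, so that release is compatible with the Day 1 start in the schedule.

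Optional: assign in enrolment order, so that 30 per arm applies to enrolled households, and keep the block size in a restricted document that still records it for the analysis.

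Cost: wording in both documents, a different list holder, and one release step per household (120 in all; sealed envelopes or a call would do). No extra households are needed.
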